### **Handling of Duplicate Diary Records**

If there is more than 1 diary record on a particular date, the first record on that date will be used in the analysis.

As some analyses require use of the primary censoring rule, assessments collected on or after the day of rescue will be excluded from the weekly visit interval calculation when implementing the rule for the daily diary. If, after exclusion of these records, there are less than 4 non-missing

assessments, the weekly interval that implements the primary censoring rule will be considered missing. The poststudy follow-up weekly score for daily diaries will be calculated as the mean of the 7 days prior to the follow-up visit that occur after last dose of study treatment.

### 6.2.2.2. Covariate Adjustment

This study will be conducted by multiple investigators at multiple sites internationally, and countries will be categorized into geographic regions (see [Table JAIN.5.1](#)). Randomization to treatment groups at Week 0 (Visit 2) is stratified by disease severity (IGA) and geographic region as described in [Section 5.1](#). Unless otherwise specified, the statistical analysis models will adjust for disease severity and geographical region.

The covariates used in the logistic model for categorical data will include the parameter value at baseline. The covariates used in the analysis of covariance (ANCOVA) model for continuous data will include the parameter value at baseline. Inclusion of baseline in the model ensures that treatment least-squares means (LSMs) are estimated at the same baseline value. When a mixed-model repeated measures (MMRM) analysis is performed, baseline value and baseline-by-visit interactions will be included as covariates.

Unless otherwise specified, all analyses described in this section will compare estimates (for example, odds ratios, LSMs, proportions) of baricitinib 4-mg, 2-mg, and 1-mg to placebo. Thus, odds ratios are for baricitinib treatment groups relative to placebo; similarly, LSM differences and differences in proportions are between baricitinib treatment groups and placebo.

### 6.2.2.3. Analysis Method

The main analysis of categorical efficacy variables and health outcomes variables will use a logistic regression analysis with region (as appropriate), baseline disease severity (IGA), baseline value, and treatment group in the model. Firth's correction will be used in to accommodate (potential) sparse response rates. The p-value for the odds ratio from the logistic regression model will be used for statistical inference, unless Firth's correction still results in quasi-separation. In that case, Fisher's exact test will be used for statistical inference. The difference in percentages and 100(1-alpha)% CI of the difference in percentages using the Newcombe-Wilson without continuity correction will be reported. The p-value from the Fisher's exact test will also be produced as a secondary analysis.

In case geographic region is used as factor in the statistical model, for the analysis of the primary endpoint, treatment-by-region interaction will be added to the logistic regression model as a sensitivity analysis and results from this model will be compared to the primary model (without the interaction effect). If the treatment-by-region interaction is significant at a 2-sided  $\alpha$  level of 0.1, the nature of this interaction will be inspected as to whether it is quantitative (that is, the treatment effect is consistent in direction across all regions but not in size of treatment effect) or qualitative (the treatment is beneficial in some but not all regions). If the treatment-by-region interaction effect is found to be quantitative, results from the primary model will be presented. If the treatment-by-region interaction effect is found to be qualitative, further inspection will be used to identify in which regions baricitinib is found to be more beneficial.

The main analysis method for all continuous efficacy and health outcomes variables will use MMRM analysis. The MMRM model will use a restricted maximum likelihood (REML) estimation. The model will include treatment, region (as appropriate), baseline disease severity (IGA), visit, and treatment-by-visit-interaction as fixed categorical effects and baseline and baseline-by-visit-interaction as fixed continuous effects.

For daily diary assessments and the model for 24-week interim analyses, the following models will be generated:

- The models include weekly assessment up to Week 16: results from this model will be used in a graphical testing scheme. If the algorithm fails to converge, the scheduled visit weeks will be used: 1, 2, 4, 8, 12, and 16.
- The models include weekly assessment up to Week 24: If the algorithm fails to converge, the scheduled visit weeks will be used: 1, 2, 4, 8, 12, 16, 20, and 24.

For daily diary assessments and the model for 52-week interim analyses:

- The models include weekly assessment up to Week 52.
- If the algorithm fails to converge, the scheduled visit weeks will be used: 1, 2, 4, 8, 12, 16, 20, 24, 32, 40, 48, and 52.

For non-daily assessments associated with a continuous endpoint such as EASI percent change from baseline, the model will use scheduled visit as covariate.

An unstructured (co)variance structure will be used to model the between- and within-patient errors. If this analysis fails to converge, the heterogeneous autoregressive [ARH(1)], followed by the heterogeneous compound symmetry (CSH), followed by the heterogeneous Toeplitz (TOEPH), followed by autoregressive [AR(1)], followed by compound symmetry (CS) will be used. The Kenward-Roger method will be used to estimate the degrees of freedom. Treatment LSM will be estimated within the framework of the MMRM using type 3 sums of squares. Differences in LSM between each dose of baricitinib and placebo (and associated p-values, standard errors, and 95% CI) will be used for statistical inference. The LSM difference, standard error, p-value, and 95% CI will be reported.

Treatment comparisons for continuous efficacy and health outcomes variables may also be made using ANCOVA for primary and key secondary objectives. When an ANCOVA model is used, the model includes region, baseline disease severity, treatment group, and baseline value.

Inclusion of baseline in the ANCOVA models ensures that treatment LSMs are estimated at the same baseline value. Treatment LSMs will be estimated within the framework of the ANCOVA using type 3 sums of squares. Reported differences in LSM and associated p-values, standard errors, and 95% CI will be used for statistical inference. Treatment-by-region interaction will also be added to the model for sensitivity purposes and is discussed in Section 6.10.

Time to event will be analyzed using cumulative incidence function with observed values, defining first time reaching the event IGA (0,1), EASI 75, or Itch NRS 4-pt improvement before rescue as onset, treating rescue and discontinuation for lack of efficacy as competing event censor up to Week 16.

Fisher's exact test will be used to test the difference between each baricitinib dose and placebo in proportion of patients experiencing AEs, discontinuation from study drug, and for other categorical safety data. Continuous vital signs, body weight, and other continuous safety variables, including laboratory variables will be analyzed by an ANCOVA with treatment group and baseline value in the model. The significance of within-treatment group changes from baseline will be evaluated by testing whether the treatment group LSM changes from baseline are different from zero; the standard error for the LSM change will also be displayed.

Differences in LSM will be displayed, with the p-value associated with the LSM comparison to placebo and a 95% CI on the LSM difference also provided. In addition to the LSMs for each group, the within-group p-value for the change from baseline will be displayed.

For the Period 3 and Period 4 efficacy and safety analysis, only descriptive statistics will be provided to both categorical and continuous endpoints. No statistical inferential test will be provided.

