5.1. Overall Design

Study I4V-MC-JAIN (JAIN) is a Phase 3, multicenter, double-blind, randomized, placebo-controlled study evaluating the safety and efficacy of baricitinib 1-mg QD, 2-mg QD, and 4-mg QD in combination with TCS in patients with moderate-to-severe atopic dermatitis (AD) who have experienced failure of cyclosporine, or are intolerant to, or have a contraindication to, cyclosporine. The study is divided into 5 periods: a 5-week Screening period, a 1-year Double-Blind Treatment period (Week 0 through Week 52), a 1-year double-blind, long-term extension (Week 52 through Week 104) that includes a randomized downtitration substudy, a bridging extension that may last up to 96 weeks (Week 104 to up to Week 200) and a 4-week Post-Treatment Follow-Up period.

Approximately 500 patients ≥ 18 years of age will be randomized at a 1:1:2:1 ratio to receive placebo QD, baricitinib 1-mg QD, baricitinib 2-mg QD, or baricitinib 4-mg QD (100 patients in the placebo group; 100 patients each in the baricitinib 1-mg and 4-mg groups; and 200 patients in the baricitinib 2-mg treatment group). Patients will be stratified at randomization according to disease severity (Investigator's Global Assessment [IGA] 3 versus 4) and geographic region if the planned country allocation justifies.

All procedures to be conducted during the study, including timing of all procedures, are indicated in the Schedule of Activities (Section 2). Section 9.4.4 describes collection of laboratory samples; [Appendix 2](#), [Appendix 4](#), and [Appendix 5](#) list the specific laboratory tests that will be performed for this study. Study governance considerations are described in detail in [Appendix 3](#). Section 10.3.7.1 outlines information regarding the data monitoring committee (DMC) and interim analyses.

[Figure JAIN.1](#) illustrates the study design.

Abbreviations: AD = atopic dermatitis; eGFR = estimated glomerular filtration rate; ET = early termination; IGA = Investigator’s Global Assessment; IP = investigational product; PPD = purified protein derivative; QD = once daily; TB = tuberculosis; TCS = topical corticosteroids; V = visit; W = week.

^a Applicable to patients taking topical treatments (excluding emollients) or systemic treatments for AD at the time of screening.

^b Maximum dose of baricitinib for patients with renal impairment (defined as eGFR <60 mL/min/1.73 m²) will be 2-mg QD.

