## 6. A Priori Statistical Methods

### 6.1. Determination of Sample Size

Study JAIN will aim to enroll 500 patients  $\geq 18$  years of age. Ignoring stratification, the proposed sample size will ensure  $>90\%$  power based on the Chi-square test to detect an absolute difference of approximately 25% between the 4-mg baricitinib and the placebo treatment group and the 2-mg baricitinib and placebo treatment group, each using a 2-sided alpha of 0.025 and assuming approximately 20% placebo response rate for the primary endpoint. These assumptions are based on what was observed in Phase 3 Study 14V-MC-JAIY.

Sample size and power estimates were obtained from nQuery® Advisor 7.0.

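### The confidence interval for the difference in response rates ignores the randomisation strata that the test adjusts for, so it is slightly conservative if those strata predict response

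*SAP*

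**What the plan says.** SAP 5.1 and 6.2.2.2 stratify randomisation by baseline IGA (3 versus 4) and by region (Europe, Japan, Rest of World). Section 6.2.2.2 adds: "Unless otherwise specified, the statistical analysis models will adjust for disease severity and geographical region". Section 6.2.2.3 then bases inference for categorical endpoints on the odds-ratio p-value from a Firth-corrected logistic regression containing region (as appropriate), IGA, baseline value and treatment.

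For the difference in percentages, the same section says: "The difference in percentages and 100(1-alpha)% CI of the difference in percentages using the Newcombe-Wilson without continuity correction will be reported". It names no strata, weights or covariates. SAP 6.14 uses the same interval for subgroups. The covariate rule in 6.2.2.2 concerns models, and a Newcombe-Wilson interval is not a model. Protocol 10.3.1 asks for the difference with a 95% interval but names no method. No stratified or adjusted risk difference is planned anywhere.

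For the primary endpoint, SAP 6.10.2 also reports the odds ratio with its 95% interval, which comes from the same model as the p-value.

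**The concern.** After stratified randomisation, part of the variation in response is balanced between arms by design. An interval built from a single two-by-two table still counts that part as sampling error, so it is too wide whenever the strata carry information about response. Continuous endpoints do not have this mismatch: in SAP 6.2.2.3 the least-squares mean difference, its interval and its p-value come from one model.

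At stake is the precision shown on the percentage scale, which is the scale of the planning assumption. In a borderline comparison, a significant adjusted p-value could also stand beside an interval that includes zero.

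**Working it through.** **Inputs from the documents.** SAP 6.1 gives "power based on the Chi-square test to detect an absolute difference of approximately 25" percentage points, "each using a 2-sided alpha of 0.025" and "assuming approximately 20% placebo response rate for the primary endpoint". Protocol 5.1 gives "100 patients in the placebo group" and "100 patients each in the baricitinib 1-mg and 4-mg groups; and 200 patients in the baricitinib 2-mg treatment group". SAP 6.1 sets the strata aside for planning: "Ignoring stratification, the proposed sample size will ensure" more than 90% power. I use the 95% level of SAP 6.10.2; section 6.2.2.3 leaves it as 100(1-alpha)%.

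**The plan's own figure.** Power = Φ[(0.25 − z × SE₀)/SE₁], with z = 2.2414 for a two-sided alpha of 0.025.
- 4-mg versus placebo (100/100): SE₀ = √(2 × 0.325 × 0.675/100) = 0.0662 and SE₁ = √(0.45 × 0.55/100 + 0.20 × 0.80/100) = 0.0638. Power is 94.4%.
- 2-mg versus placebo (200/100): SE₀ = 0.0590, SE₁ = 0.0533. Power is 98.6%.

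Both exceed 90%, so the stated power reproduces.

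**The planned interval at the planning rates.** The 95% Wilson limits are 0.356 to 0.548 for 45/100 and 0.133 to 0.289 for 20/100. Newcombe combines them:
- lower limit: 0.25 − √[(0.45 − 0.356)² + (0.289 − 0.20)²] = 0.121
- upper limit: 0.25 + √[(0.548 − 0.45)² + (0.20 − 0.133)²] = 0.368

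The width is 24.7 points. For 2-mg versus placebo the interval is 13.9 to 34.6 points, width 20.8.

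**What stratification could save: IGA alone.** The documents give no stratum-specific response rates, so these are assumptions. Take two equal IGA strata with response p ± s. The average within-stratum variance is p(1 − p) − s², so with 100 per arm the stratified variance is (0.2475 − s₁²)/100 + (0.16 − s₀²)/100. The crude variance is 0.004075.

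| Spread s₁ (active) / s₀ (placebo), points | Stratified variance | SE | Ratio to crude |
|---|---|---|---|
| 0 / 0 | 0.004075 | 0.0638 | 1.000 |
| 5 / 5 | 0.004025 | 0.0634 | 0.994 |
| 10 / 10 | 0.003875 | 0.0622 | 0.975 |
| 15 / 10 | 0.003750 | 0.0612 | 0.959 |
| 20 / 15 | 0.003450 | 0.0587 | 0.920 |

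**IGA and region together.** Six strata, with half the patients at each IGA level and regions split 50/25/25 (assumed). The stratified SE is about 0.0628 for severity/region odds ratios of 2/1.5, 0.0617 for 3/1.5 and 0.0603 for 4/2. That is 1.6% to 5.5% below 0.0638. Other region patterns gave 1.5% to 6.5%.

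**Coverage and width.** In simulated trials with six strata and 100 per arm:
- The crude interval covered about 95.3% to 96.2% for severity odds ratios of 2 to 4 and region odds ratios of 1.5 to 2. It was about nominal when the strata had no effect.
- A Mantel-Haenszel difference with a stratified variance was 2% to 5% narrower at odds ratios of 3/1.5 to 4/2, with coverage near 95%.
- The stratified Newcombe form based on pooled stratified Wilson limits was 1.00 to 1.015 times the crude width, so it saved nothing.

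**Agreement between test and interval.** Simulated at two-sided 0.05, Firth logistic p-value against the crude interval:
- 20% versus 45%: they disagree in 0.0% to 0.8% of trials.
- 20% versus 35%: about 2% with non-prognostic covariates, 2% to 4% with moderately prognostic ones, and 8% to 11% with strongly prognostic ones.

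**The case against.** The strongest reply is that nothing inferential changes. The logistic p-value alone decides each hypothesis, SAP 6.10.2 already gives an adjusted interval on the odds-ratio scale, and the crude difference has the merit of equalling the gap between the two reported percentages. All of that stands, and it limits the point to a matter of reporting. It does not supply an adjusted interval on the percentage scale.

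Three stronger readings are tempting, and the documents do not support them.
- *The trial wastes patients.* A 1.6% to 5.5% smaller SE looks like 3% to 12% more patients, since (0.0638/0.0628)² = 1.03 and (0.0638/0.0603)² = 1.12. But power comes from the adjusted test, and only the width of a displayed interval is affected.
- *The crude interval always over-covers.* It does so only if the strata predict response, which the documents do not show.
- *Stratifying the interval would make it agree with the test.* The test also adjusts for baseline value, uses Firth's correction and works on the odds scale. Some disagreement appears even with non-prognostic covariates, then mostly with the interval excluding zero while p is not significant. In one set of simulations at 20% versus 35%, disagreement was 4.7% with the crude interval and 4.85% with either of two stratified Newcombe forms.

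A further fair objection is that the gain at 20% versus 45% does not carry over to every endpoint. With odds ratios of 3/1.5 and regions split 60/20/20, the SE gain is 3.6% at 20% versus 45%, 2.6% at 10% versus 25%, and 1.8% at 5% versus 15%. The low-response endpoints also have the sparsest strata.

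**Conclusion.** The mismatch is in the text and the point holds at a minor level. Under the assumed stratum effects above, the crude interval for 4-mg versus placebo is roughly 1% to 5% too wide, or about 0.2 to 1.2 points of 24.7, with coverage up to about 96.2%. The size rests entirely on assumed odds ratios and stratum shares, and it is zero if IGA and region are not prognostic. Type I error and power are untouched. Disagreement between test and interval is rare at the planned effect; a better interval would at most reduce it, not remove it.

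**What to change.** In SAP 6.2.2.3, add a risk difference that uses the randomisation strata. Either of these will serve:
- the Mantel-Haenszel difference over IGA × region, Σwₖ(p₁ₖ − p₀ₖ)/Σwₖ with wₖ = n₁ₖn₀ₖ/(n₁ₖ + n₀ₖ), with a stratified (Sato-type) variance; or
- the risk difference standardised from the planned logistic model, with a delta-method or bootstrap interval.

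Do not specify the stratified Newcombe form built on pooled stratified Wilson limits, which gives no narrowing. Keep the crude Newcombe-Wilson interval as a secondary display.

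Write the region-pooling rule as well. SAP 5.1 says small regions may be combined and refers to 6.2.2.2 for details, but 6.2.2.2 contains neither a rule nor a minimum number. Without it the strata are undefined.

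The cost is some wording and one extra display, plus care with sparse strata for low-response endpoints. SAP 6.16 records that the Week 24 analysis has been conducted, and Protocol 10.3.1.3 makes that the primary analysis. For those results the new interval should therefore be labelled supplementary and should not replace the planned one.

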### **6.2.3. Derived Data**

- Age (year), derived using first dose date as the reference start date and July 1 of birth year and truncated to a whole-year (integer) age. Patients whose derived age is less than 18 will have the required minimum age of 18 at informed consent; however, reporting for age, age groups, and laboratory ranges, will be based on the derived age.
- Age group (<65 years,  $\geq$ 65 years)
- Age group (<65 years,  $\geq$ 65 years to <75 years,  $\geq$ 75 years to <85 years,  $\geq$ 85 years)
- Body mass index (BMI) ( $\text{kg}/\text{m}^2$ ) = weight ( $\text{kg}$ )/((height ( $\text{cm}$ )/100) $^2$ )
- BMI category (<25  $\text{kg}/\text{m}^2$ ,  $\geq$ 25  $\text{kg}/\text{m}^2$  to <30  $\text{kg}/\text{m}^2$ ,  $\geq$ 30  $\text{kg}/\text{m}^2$ )
- The duration of AD from diagnosis (years) = [(date of informed consent – date of AD diagnosis )+1]/ 365.25.
  - If year of onset is missing, duration of AD will be set as missing. Otherwise, unknown month will be taken as January, and unknown day will be taken as 01. The duration of AD will be rounded to 1 decimal place.
- Duration of AD (years) category (0 to <2 years, 2 years to < 5 years, 5 years to <10 years, 10 years to <20 years,  $\geq$ 20 years)
- Diagnosis age (years), derived using diagnosis date as the reference start date and July 1 of birth year and truncated to a whole-integer age
- Diagnosis age group (<18,  $\geq$ 18 to <50,  $\geq$ 50 years old)
- Change from baseline = postbaseline measurement at Visit x – baseline measurement
  - If a baseline value is missing, it will not be imputed and the change from baseline will not be calculated.
- Percent change from baseline at Visit x:  
((postbaseline measurement at Visit x - baseline measurement)/baseline measurement)\*100.
  - If a baseline value is missing, it will not be imputed and percent change from baseline will not be calculated.
- Weight ( $\text{kg}$ ) = weight ( $\text{lb}$ ) \* 0.454.

- Weight category (<60 kg,  $\geq$ 60 kg to <100 kg,  $\geq$ 100 kg)
- Height (cm) = height (in) \* 2.54.
- Cyclosporine inadequate efficacy (yes, no)
  - Set **yes** if the reason for discontinuation is inadequate response.
- Cyclosporine intolerance (yes, no)
  - Set **yes** if the reason for discontinuation is intolerance to medication or contraindication (physician indicated cyclosporine was used and a contraindication was noted).
- Cyclosporine contraindication [ineligible] (yes, no)
  - Set to **yes** if cyclosporine never used because of a contraindication
- Cyclosporine inadvisable (yes, no)
  - Set to **yes** if the following reasons were selected for either not using the medication or discontinuing the medication:
    - Reason for not using medication: physician decision, concern about side effects, unfavorable benefit risk, contraindication
    - Reason for discontinuation: inadequate response, intolerance to medication, or contraindication
- Topical calcineurin inhibitor (TCNI) inadequate efficacy (yes, no)
  - Set **yes** if the reason for discontinuation is inadequate response.
- TCNI intolerance (yes, no)
  - Set **yes** if the reason for discontinuation is intolerance to medication or contraindication (physician indicated TCNI was used and a contraindication was noted).
- TCNI contraindication [/ineligible](yes, no)
  - Set to **yes** if TCNI never used because of a contraindication
- TCNI inadvisable (yes, no)
  - Set to **yes** if the following reasons were selected for either not using the medication or discontinuing the medication:
    - Reason for not using medication: physician decision, concern about side effects, unfavorable benefit risk, contraindication
    - Reasons for discontinuation: inadequate response, intolerance to medication, or contraindication.

### 6.3. Handling of Dropouts or Missing Data

Intercurrent events (ICH E9 R1) are events which occur after the treatment initiation and make it impossible to measure a variable or influence how it would be interpreted.

Depending on the estimand being addressed, different methods will be used to handle missing data as a result of intercurrent events. Intercurrent events may occur through the following:

- application of one of the censoring rules (including after permanent study drug discontinuation, after rescue therapy, or re-treatment)
- discontinuation of inadvertently enrolled patients

- discontinuation from the study due to enrollment in other trials, medical, safety or regulatory reasons, investigator decision, and patient decision
- missing an intermediate visit prior to discontinuation, rescue, or re-treatment
- loss to follow-up

Noncensor intercurrent events are events that are not due to the application of any censoring rule, that is, the last 4 items in the list above.

Note that as efficacy and health outcome data can accrue after a patient permanently discontinues study drug or begins rescue therapy, specific general censoring rules to the data will be applied to all efficacy and health outcome observations subsequent to these events depending on the estimand being addressed. These specific censoring rules are described below.

The *primary censoring rule* will censor efficacy and health outcome results after permanent study drug discontinuation or after rescue therapy. This censoring rule will be applied to all continuous and categorical efficacy and health outcome endpoints.

A *secondary censoring rule* will only censor efficacy and health outcome results after permanent study drug discontinuation. As a consequence, data for patients rescued with high or ultra-high potency TCS or with phototherapy will not be censored at the time of rescue as they can continue or only temporarily interrupt study drug. As patients who are rescued to systemic corticosteroids are required to permanently discontinue study drug, they will also have post-rescue observations censored. The secondary censoring rule will be applied to primary and key secondary efficacy and health outcome endpoints. The secondary censoring rule will be applied to all endpoints at Week 52 as the main analyses.

For **Long-Term Extension(LTE) Substudy analysis**, the censoring rule will censor the efficacy and health outcome results after permanent study drug discontinuation or after the retreatment, whichever occurred first.

For **Long-Term Extension(LTE) Non-responder analysis** the censoring rule will censor the efficacy and health outcome results after permanent study drug discontinuation.

For **Time to Relapse analysis**, if Relapse (IGA $\geq 3$  in Period 3 or Period 4) occurred on or after permanent study drug discontinuation, the event would be censored on the last available visit date.

For **Long-Term Extension (LTE) Responders & Partial Responders who did not enter the Substudy** the censoring rule will censor the efficacy and health outcome results after permanent study drug discontinuation or after the dose change, whichever occurred first.

Nonresponder imputation (for categorical variables) and MMRM (for continuous variables) will be the primary methods used to handle missing data. Sections 6.3.1 through 6.3.5 summarize the imputation methods for the various efficacy and health outcome endpoints.

